**Patiromer Efficacy to Reduce Episodic Hyperkalemia in End Stage Renal Disease Patients
Treated with Hemodialysis (PEARL-HD)**

Protocol May 17, 2019

PI: [name]

NCT03781089

1. Protocol Summary Synopsis

Name of Sponsor: Relypsa

Name of product: Patiromer

Title of Study: Patiromer Efficacy to Reduce Episodic Hyperkalemia in End Stage Renal Disease Patients Treated with Hemodialysis (PEARL-HD)

Study Center: Duke University

Study Period (weeks): 7

Study design: Prospective randomized open label trial

Primary objective: To determine if patiromer administered orally once a day with the morning or mid-day meal will reduce the frequency of episodes of hyperkalemia in ESRD patients who receive thrice-weekly HD.

Secondary objectives:

1. To determine whether patiromer can effectively be used in place of one dose of phosphate binder per day
2. To determine the between-group differences in percent of patients with serum K > 5.5 mEq/L
3. To determine the efficacy and dosing of patiromer in ESRD patients.
4. To determine the between-group differences in need for additional hemodialysis treatments due to hyperkalemia
5. To determine the between-group differences in pre-specified significant arrhythmia events as detected with cardiac monitors in Week 4.
6. To determine the between-group differences in serum albumin and PTH concentrations.
7. To determine feasibility of a large-scale hemodialysis-based trial.
8. To determine the change in serum potassium concentration two weeks after study drug is discontinued
9. To determine the change in serum phosphorus concentration two weeks after study drug has been discontinued
10. To develop procedures and instruments to be employed in a large scale clinical trial.

Planned enrollment: 40

Inclusion criteria:

1. Males and Females, age at least 18 years
2. End-stage renal disease treated with thrice-weekly hemodialysis for \geq 3 months.
3. At least two measured pre-dialysis serum [K] \geq 5.5 mEq/L or one [K] \geq 6.0 mEq/L noted over the past three months
4. Current use of dialysate with potassium concentration = 2 mEq/L
5. Typical consumption of at least two meals per day
6. Have received customary dietary instruction over prior month
7. Considered by the treating physician(s) to be in otherwise stable clinical condition.
8. If patient is of childbearing potential, he/she will be willing to avoid pregnancy during the study using an acceptable birth control method.

Exclusion Criteria:

1. Not considered by the treating physician(s) to be adherent with recommended dialysis schedule and prescribed medications
2. Life expectancy < 3 months
3. Currently prescribed oral potassium supplements
4. Therapy with oral potassium-lowering medication in the prior three months,
5. Underlying severe gastrointestinal disorders, including history of ischemic bowel.
6. Corrected serum calcium concentration > 10.5 mg/dL in prior three months
7. Anticipated kidney transplant within the next 3 months
8. Prisoners or others who are involuntarily incarcerated or detained
9. Pregnant, breastfeeding, or considering pregnancy.
10. Participation in a clinical trial of an experimental treatment within the past 30 days

Duration of treatment:

Participants randomized to receive patiromer will receive the drug for a total of 4 weeks.

Withdrawal of subjects

Subjects will be withdrawn from the study and receive appropriate treatment for hyperkalemia (at the Investigator's discretion), if the serum potassium level exceeds 7 mEq/L during Week 2 to 7 and, the first sample is confirmed by a second sample exceeding 7 mEq/L at an unscheduled visit within one week.

Concomitant medications:

Subjects are not allowed to receive potassium binders during the study (e.g. sodium polystyrene sulfonate, or SPS) except in emergency situations.

Except for those listed in the exclusion criteria, all medications (prescription or over-the-counter) that have been started prior to screening may be continued during the course of the study.

Statistical analysis:

This is a proof-of-concept study, to determine the extent to which administration of patiromer has the potential to change the risk category for ESRD patients who are on conventional HD schedules. In addition, the study aims to develop and test study procedures and instruments that will be implemented in a large-scale clinical trial.

By nature of the size of the study, the power of the trial will be limited. The proposed primary endpoint is the between-group differences of the number of episodes, per subject, of serum K \geq 5.5 mEq/L during Weeks 3 and 4. This will be assessed as follows: Six serum samples will be collected and assessed for each patient during the efficacy phase (Weeks 3 and 4). Patients would receive a score of perfect K control (6 of 6 samples in range; Score 1.0), moderate K control (5 of 6 in range; Score 0.83), inconsistent K control (4 of 6 in range; Score 0.67), erratic K control (3 of 6 in range; Score 0.50), poor K control (2 of 6 in range; Score 0.33), very poor K control (1 of 6 in range; Score 0.17), or no K control (0 of 6 in range, Score 0). These scores will then

be averaged for the patients in the active treatment group and the control group, and the results will be compared. Using this approach, a sample size of n=20 per group provides 86% power to detect a between-group difference of 2 in mean episodes of hyperkalemia per patient, assuming $\alpha=0.05$ and standard deviation 2.

Exploratory endpoints, including those derived from the cardiac monitors, will be assessed by comparison of means and standard deviations between the two groups.

[figure not shown]
Safety Variables

Safety and tolerability variables will consist of adverse events, vital signs, ECG-parameters, clinical laboratory parameters and physical examination. Adverse Events will be summarized in an incidence table and coded to MedDRA. Laboratory parameters, vital signs and ECG-parameters will be summarized; the changes in the hematology, biochemistry parameters and vital signs from baseline will also be presented. Serious Adverse Events (SAE's) will be reported on a jointly developed form with Relypsa.

Efficacy Variables

Efficacy parameters will consist of serum levels of potassium, collected prior to scheduled dialysis treatments.

2. Study Flowchart

3. Introduction and Study Rationale

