It is important to review standard, usual care for ESRD patients who are treated with conventional HD schedules (thrice-weekly treatments), to avoid and treat episodes of hyperkalemia. If patients present at an emergency facility or hospital and are discovered to have hyperkalemia, they are typically treated with inhaled beta agonists, intravenous glucose and insulin, and/or intravenous calcium ²⁴. The latter does not treat the hyperkalemia *per se*, but it is intended to stabilize the myocardial cells and limit risk of depolarization. A single dose of SPS is often administered. If these medical interventions fail to resolve hyperkalemia, urgent hemodialysis is prescribed. In the outpatient setting, hyperkalemia may be detected at the start of the HD session. If there are no symptoms, patients receive hemodialysis with their usual prescriptions and no further interventions are prescribed. For all patients, the HD clinic-based dietitian will counsel on adherence with a low potassium diet, with the goal of limiting potassium intake to less than 60 mEq per day ^{25,26}. For this current protocol, the dietitian will be blinded to the assigned treatment for the course of the study. If pre-dialysis hyperkalemia is a recurrent problem, the physician and dialysis clinic team will review the prescribed dialysate. Due to the risk associated with prescription of low dialysate potassium, the outpatient clinics employed in this study do not prescribe dialysate potassium lower than 2 mEq/L. In rare instances, if hyperkalemia continues to recur despite these interventions, and additional HD treatments will be prescribed.

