4.2 Secondary endpoints

1. To determine whether patiromer can effectively be used in place of one dose of phosphate binder per day
2. To determine the between-group differences in percent of patients with serum $K > 5.5$ mEq/L
3. To determine the efficacy and dosing of patiromer in ESRD patients.
4. To determine the between-group differences in need for additional hemodialysis treatments due to hyperkalemia
5. To determine the between-group differences in pre-specified significant arrhythmia events as detected with cardiac monitors in Week 4.
6. To determine the between-group differences in serum albumin and PTH concentrations.
7. To determine feasibility of a large-scale hemodialysis-based trial.
8. To determine the change in serum potassium concentration two weeks after study drug is discontinued
9. To determine the change in serum phosphorus concentration two weeks after study drug has been discontinued
10. To develop procedures and instruments to be employed in a large scale clinical trial.

5. Selection and withdrawal of subjects

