8.2 Secondary endpoints

Because study sample size is limited and is based only on the amount of information needed to adequately assess the primary hypothesis, this pilot study will have limited power to effects on secondary endpoints. We consider these measurements to be exploratory. A significant effect on the exploratory endpoints will be considered in light of the results of the primary analysis.

Differences in laboratory values between the treatment groups will be determined by analysis of variance (ANOVA). The long-term heart monitor results will be compared in the following ways:

Group 1: Individual patient compared by their LTHM #1 vs LTHM #2;

Group 2: Individual patient compared by their LTHM #1 vs LTHM #2

Group 1 LTHM #1 vs Group 2, LTHM #1;

Group 1 LTHM #2 vs Group 2, LTHM #2

Each monitor will be assigned a point score, counting only the most severe event.

Finding	Score
Sustained VT, VF and/or asystolic cardiac arrest (CPR required)	10
Nonsustained VT (\geq 3 beats but $<$ 30 seconds) and/or $>$ 5 second pause during daytime (0800-2000) and/or atrial fibrillation ($>$ 30 seconds)	3
PVC $>$ 1000/24h and/or $>$ 3 second pause during daytime (0800-2000)	2
PVC $>$ 500/24h and/or or HR $<$ 40 for 5 consecutive beats during daytime (0800-2000)	1

Monitor period scores will be tabulated, and differences in period scores addressed by ANOVA.

Heart rate variability will be recorded in time-domains from the LTHM and periods will be compared.

The QT intervals will be compared for the LTHM periods in two different procedures. The mean QTc will be determined for each 7 day period, and groups will be compared. In addition, in the LTHM will collect 30 second rhythm strips in the last dialysis session (HD3) of week 4, and QTc will be determined and compared between the treatment groups.

Bradyarrhythmias will be recorded and classified for comparison as follows: asystole > 5 seconds with syncope, third degree AV block, second degree AV block, sinus pause > 3 seconds, and sinus bradycardia < 40 bpm.

9. Monitoring

The sponsor of the study, Relypsa, will provide study monitoring at a mutually agreeable time, during normal business hours.

10.. Schedule of Assessments

Procedures/Visits	Pre- Week 0	Week 0			Week 1			Week 2			Week 3			Week 4		
		Visit	HD1	HD2	HD3	HD1	HD2									
Week		1		2		3		4		5						
Determination of Elevated K Episodes	X															
Informed Consent	X															
Medical History and Demography		X														

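### Comparing means and SDs does not convey the uncertainty of the yes/no exploratory endpoints at 20 per arm, and no method for proportions is given

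*Combined protocol and SAP*

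**What the plan says.** The Statistical analysis part of the synopsis sets one rule, with no exception by type of endpoint: "Exploratory endpoints, including those derived from the cardiac monitors, will be assessed by comparison of means and standard deviations between the two groups". Section 8.2 says of the secondary endpoints: "We consider these measurements to be exploratory". Read together, the synopsis rule reaches the secondary endpoints.

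Section 8.2 adds ANOVA for laboratory values and for the cardiac-monitor point score. It names no method for a proportion. The only incidence table planned is for adverse events.

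Three sets of endpoints are naturally yes/no per patient:

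- Secondary objective 2: "To determine the between-group differences in percent of patients with serum K > 5.5 mEq/L". No sampling window is attached to it.
- Secondary objective 4: "To determine the between-group differences in need for additional hemodialysis treatments due to hyperkalemia". This can be read as any versus none, or as a count of sessions. Section 3.3 describes when usual practice adds sessions: "In rare instances, if hyperkalemia continues to recur despite these interventions". No rate is given.
- The bradyarrhythmia list in section 8.2: "Bradyarrhythmias will be recorded and classified for comparison as follows". Five classes follow, including third degree AV block, with no method for the comparison.

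**The concern.** Means and SDs suit QTc, heart rate variability and laboratory values. For a 0/1 variable the SD is a function of the proportion, so printing it beside the proportion adds no information. Near 0 of 20 or 20 of 20 it shrinks to nothing just when the data say least about the true rate. An arm with no extra dialysis, or no third degree AV block, would be summarised as 0 (SD 0), which invites a reading of certainty. The study is a proof of concept meant to prepare a large-scale trial, so a reader may well take these summaries forward as planning rates.

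**Working it through.** **Inputs.** From the plan: 20 patients per arm (synopsis and section 8.1) and 1:1 allocation (section 6.6). The plan gives no event rate for any of the yes/no endpoints, so every rate below is an assumption, shown over a range.

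**The plan's own figure.** It says that "a sample size of n=20 per group provides 86% power" for a "between-group difference of 2 in mean episodes of hyperkalemia per patient" with SD 2 and α 0.05. With a two-sided two-sample t-test, the noncentrality is (2/2)·√(20/2) = 3.16 on 38 degrees of freedom and the power is 86.9%, which agrees. This concerns the primary endpoint only. No figure is stated for the exploratory endpoints.

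**SD of a yes/no variable.** SD = √[n/(n−1) · p̂(1−p̂)].

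- 0/20: SD = 0.
- 1/20: SD = √[(20/19)(0.05)(0.95)] = 0.224.

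Both are correct, and both follow from the count alone.

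**What 0/20 allows.** Exact 95% upper limit: 1 − 0.025^(1/20) = 16.8%. Wilson upper limit: 1.96²/(20 + 1.96²) = 3.84/23.84 = 16.1%.

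**How often an arm has no events.** (1−p)^20 for one arm, and 1 − [1 − (1−p)^20]² for at least one of two arms with equal rates:

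| Assumed rate | Given arm has none | At least one arm has none |
|---|---|---|
| 2% | 67% | 89% |
| 5% | 36% | 59% |
| 10% | 12% | 23% |

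**One-arm interval built from the SD.** Coverage of p̂ ± t(19)·SD/√20, nominal 95%, summed over Binomial(20, p): 33% at a rate of 2%, 64% at 5%, 88% at 10%, 92% at 20%, 96% at 50%.

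**Interval for the difference between arms.** Coverage of the pooled-t interval (38 degrees of freedom), summed over both binomials:

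| Assumed rates | Pooled-t interval | Newcombe interval |
|---|---|---|
| 5% vs 0% | 64% | above 99% |
| 5% vs 1% | 70% | above 99% |
| 10% vs 2% | 87% | 99% |
| 20% vs 5% | 94% | 96% |
| 20% vs 10% | 94% | 97% |
| 5% vs 5% | 99% | above 99% |

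The shortfall at 5% vs 1% comes almost wholly from tables with no events in either arm. Their probability is (0.95 × 0.99)^20 = 29%, and the t interval is then the single point 0, which misses the true 4 points. For 0/20 vs 0/20 the Newcombe interval is ±√(0.161² + 0²), or about −16 to +16 points.

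**Type I error of the t-test.** At equal true rates of 2%, 5%, 10%, 20%, 30% and 50% it is 0.1%, 1.2%, 3.9%, 5.0%, 5.3% and 4.3%. It is not materially inflated.

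**Objective 2.** If the endpoint is any high value among the six samples of Weeks 3 and 4 (an assumption), a beta-binomial model gives these control-arm proportions for within-patient correlation from 0.375 down to 0:

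- per-sample rate 20%: 47% to 74%
- per-sample rate 40%: 75% to 95%
- per-sample rate 50%: 84% to 98%

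**The case against.** Four points on the other side deserve weight.

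- **The SD is not wrong.** A reader might infer that the planned rule yields an incorrect spread. It does not: the SD of 0/1 data is correct, only uninformative. The plan also promises no confidence interval for these endpoints, so the coverage figures describe what happens if someone builds one from the reported summaries. This stands, and it narrows the point.
- **The comparison between arms is mostly sound.** Objectives 2 and 4 concern between-group differences, and for equal or commoner rates the difference interval covers at or near 95%. This stands for those rates. It fails for rare, unequal rates, which is where extra dialysis and high-grade block may lie.
- **Single tables can mislead.** For 0/20 vs 4/20 the t interval is 1.4 to 38.6 points (p = 0.036) and the Newcombe interval is −0.05 to 41.6 points. A reader might infer that the t-test yields a false positive. Valid exact tests disagree on this table (Fisher 0.106, Boschloo 0.061, Barnard 0.039), so it is borderline and proves nothing.
- **Objective 2 need not sit near a ceiling.** A reader might take the 40 to 50% in section 3.1 as a per-sample rate and conclude that nearly every control patient will have a high value. That figure is the share of patients whose hyperkalemia persists to the next month on routine testing. With the 20% per-measurement rate of section 3.1 (general hemodialysis patients), the proportion is 47% to 74%.

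It can also be said that objective 2 already names a percentage as its summary, and that classifying bradyarrhythmias suggests tabulation. Neither supplies a measure of uncertainty or a method of comparison.

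**Conclusion.** The point holds in a limited form. The plan applies means and SDs to all exploratory endpoints, includes yes/no endpoints among them, and gives no method for proportions. For those endpoints the SD adds nothing, and at 0/20 it hides that a rate up to 16.8% is still compatible with the data. Intervals built from it cover about 64% to 87% at assumed rates of 5% vs 0% to 10% vs 2%, and have zero width when neither arm has an event.

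The size rests on assumed event rates. The documents offer only the remark that extra sessions are rare in usual practice, and nothing for the bradyarrhythmia classes. The effect on objective 2 depends on its unstated window, the per-sample rate and the within-patient correlation. The endpoints are exploratory and the primary analysis is untouched, so the impact is modest. The change is still worth making because it costs almost nothing.

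**What to change.** Limit the means-and-SD sentence in the synopsis to continuous endpoints and the monitor point score, which keeps its ANOVA from section 8.2. Add to section 8.2:

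*For yes/no endpoints (objective 2, any additional dialysis for hyperkalemia, each bradyarrhythmia class), report n/N per arm with exact or Wilson 95% limits and the risk difference with a Newcombe 95% CI. Tabulate the number of extra dialysis sessions per patient (0, 1, 2 or more) and the total per arm.*

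A table of counts is preferable to median and range for the sessions, since for a rare event the median would be 0 in both arms. State the sampling window for objective 2 in the same place.

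Cost: a few lines of plan wording and code, and no new data. Some intervals will be wider and some nominal results less favourable.

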3.5 Adverse events with patiromer

In the published clinical trial of patiromer that was the longest duration (52 weeks), hypomagnesemia (7.2%) was the most common treatment-related adverse event, mild to moderate constipation (6.3%) was the most common gastrointestinal adverse event, and hypokalemia (<3.5 mEq/L) occurred in 5.6% of patients ²⁸.

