Randomization ¹			X													
Initiation of Patiromer ²				X												
Patiromer titration ³					X			X				X		X		
Physical Exam		X														
Vital Signs ⁴ (BP, HR, Height, Weight)		X			X				X			X		X		X
Renal Function Panel		X														
Serum Potassium			X	X	X				X			X	X	X	X	X
Serum Magnesium		X							X			X				X
Serum Pregnancy Test ⁵		X														
Holter Monitor Applied	X															X
Holter Monitor Removed			X													
Previous medication and concomitant medication		X	X	X	X				X			X		X	X	X
Adverse Event Questioning		X	X	X	X				X			X		X	X	X
Dialysis ⁶																
ECG	X	←								→						

1=Randomization can occur at any point after Week 0 HD1 as long as it is completed prior to Week 0, HD3.

2=If randomized to the Patiromer Arm

3=Patiromer will be increased by 8.4 g/day if K \geq 5.1 mEq/L, decreased by 8.4 g/day if K<4.0 mEq/L, and discontinued if K<3.5mEq/L

4= Blood Pressure taken after sitting for 5 minutes; Height only collected at Week 0, HD1

5=Females of child bearing potential

6= Hemodialysis should be performed 3 times per week

BIBLIOGRAPHY

6. System USRD. 2017 USRDS annual data report: Epidemiology of kidney disease in the United States. Bethesda, MD: National Institutes of Health, National Institute of Diabetes and Digestive and Kidney Diseases; 2017.

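### No per-arm count of patients with low potassium or low magnesium is prespecified, so a low potassium can score as control and a low magnesium may be missed

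*Combined protocol and SAP*

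**What the plan says.** **Harms named.** Section 3.5, citing a 52-week trial, states that "hypomagnesemia (7.2%) was the most common treatment-related adverse event" and that "hypokalemia (<3.5 mEq/L) occurred in 5.6% of patients". Section 3.1 reports that cardiac-arrest risk rose both above and below a pre-dialysis potassium of 5.1 mEq/L, and concludes that extremes should be avoided.

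**Analyses planned.**
- Laboratory safety (synopsis, Safety Variables): parameters are summarised, and "the changes in the hematology, biochemistry parameters and vital signs from baseline will also be presented".
- Between-group laboratory differences (section 8.2): ANOVA.
- Exploratory endpoints (synopsis): these "will be assessed by comparison of means and standard deviations between the two groups".
- Adverse events (synopsis): "Adverse Events will be summarized in an incidence table and coded to MedDRA". The method of capture in the section 10 schedule is a row headed "Adverse Event Questioning".
- Potassium (synopsis, Efficacy Variables): "Efficacy parameters will consist of serum levels of potassium, collected prior to scheduled dialysis treatments". The primary endpoint (section 8.1) is the number of episodes at or above 5.5 mEq/L in Weeks 3 and 4, scored as the share of six samples in range. The range has no stated lower limit.

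**Where thresholds appear.** Secondary objective 2 counts patients, but only above 5.5 mEq/L. The withdrawal rule in section 6.15 uses an upper limit of 7 mEq/L. Low-potassium levels appear only as dose rules, and these disagree. Sections 6.7, 6.13 and 6.14 discontinue patiromer below 4 mEq/L; footnote 3 of the section 10 schedule discontinues below 3.5 mEq/L.

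**The concern.** Low potassium and low magnesium are harms of the tail: a few patients cross a limit while most do not. Changes from baseline and ANOVA describe the centre of the distribution and are poor at showing this. For potassium there is a second difficulty. It is the efficacy variable, so a patient driven too low contributes non-episodes and a lower mean, and both look like success.

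The trial asks whether patiromer can change patients' risk category, and it is meant to shape a larger trial. By the protocol's own rationale, risk lies on both sides of the potassium range. A result that reports only the upper side cannot show whether fewer high values came at the price of low ones, and the larger trial may inherit the same gap.

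**Working it through.** **1. The plan's own figure.** Difference 2, SD 2 and n = 20 per group give a standardised difference of 2/2 = 1.0. A two-sided t-test at 0.05 then has 86.9% power, against the stated 86%. The figure reproduces and is not at issue.

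**2. How a low potassium scores.** Take a patient whose six samples are all 3.4 mEq/L (an illustration).
- Episodes at or above 5.5: 0.
- Score if the range has no lower limit: 6/6 = 1.0, perfect control.
- Score if the lower limit were, say, 3.5: 0/6 = 0.

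The score agrees with the episode count through episodes = 6 × (1 − score). Without a lower limit this gives 6 × (1 − 1) = 0, which matches. With one it gives 6 × (1 − 0) = 6, which does not. An upper limit alone is therefore the natural reading, although the text does not exclude a lower one.

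**3. What the mean shows.** If one of 20 patients falls from 5.5 to 3.4 mEq/L (illustrative values), the arm mean moves by (5.5 − 3.4)/20 = 0.105 mEq/L. That is about a quarter of the 0.4 mEq/L mean fall reported in the haemodialysis study in section 3.4 (0.105/0.4 = 0.26), and in the same direction.

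**4. How many cases to expect among 20 treated patients.** The only rates available, 5.6% and 7.2%, come from 52 weeks in patients with chronic kidney disease who were not on haemodialysis. Carrying them into four weeks of haemodialysis is an assumption, so a range is shown. Expected cases = 20p; chance of at least one = 1 − (1 − p)^20. The constant-hazard row uses p = 1 − (1 − rate)^(4/52).

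| Assumption | Low K: expected; P(≥1) | Low Mg: expected; P(≥1) |
|---|---|---|
| Constant hazard over 52 weeks | 0.09; 8% | 0.11; 11% |
| Quarter of the rate | 0.28; 25% | 0.36; 30% |
| Full rate | 1.12; 68% | 1.44; 78% |
| Twice the rate | 2.24; 91% | 2.88; 96% |

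The documents do not say which row applies. Events concentrated early in treatment would raise the first row.

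**5. What a count could show.** With 0 of 20, the exact two-sided 95% upper limit is 1 − 0.025^(1/20) = 16.8%. Against zero control cases, the smallest split reaching p ≤ 0.05 by Fisher's exact test is 5 of 20 versus 0 of 20. At the full rates and no control cases, power is 0.4% (potassium) and 1.2% (magnesium). The counts can only describe.

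**The case against.** **The adverse-event table is a second route.** This stands. The 7.2% for magnesium is itself an adverse-event figure, so a reader who infers that the harms are analysed only through means and ANOVA goes too far. The text also says that laboratory values are summarised, which neither promises nor excludes minima or abnormal counts. What remains is that nothing requires a low laboratory value to be recorded as an event, and questioning need not detect a silent one.

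**Open-label reporting need not favour the drug.** This also stands. Only patiromer patients have a dose action for low potassium. Extra attention there would more likely over-count low potassium on patiromer than hide it. The documents support only that recording may be uneven by arm.

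**Magnesium cannot be read as efficacy.** Correct. A reader might infer that either harm turns into benefit, but magnesium enters no efficacy variable or score. A low value may be missed; it is not credited.

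**The size is uncertain.** Quoting 68% and 78% alone would carry 52-week rates unchanged into four weeks. Nor can the expected share of low samples be taken from a normal curve fitted to section 3.1. Fitting 9% below 4.0 and 20% at or above 5.5 gives mean 4.92 and SD 0.69, which implies 5.8% at or above 6.0. The same sentence of the protocol reports about 12.5%.

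**The low-side evidence is mixed.** Section 3.1 also reports lowest risk at 4.6 to 5.3 and at 4 to 5.5 mEq/L. That argues against treating every value below 5.1 as a harm, but not against counting values below 3.5, the cut given in section 3.5.

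**Conclusion.** The gap is real but modest. The plan prespecifies no per-arm count of patients with low potassium or low magnesium. On the natural reading of the primary endpoint, a low potassium counts as control and lowers the arm mean. A low magnesium may be missed. Apart from the laboratory summaries, both harms depend on an adverse-event table with no rule for laboratory values.

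The consequence cannot be sized closely: the chance of at least one case among 20 treated patients runs from 8% to 91% for potassium and from 11% to 96% for magnesium across the assumptions shown. Formal comparison is out of reach. The documents do not support the inference that the primary score is invalid or that harm would necessarily be concealed. The case for change rests on method: a laboratory-based count below a threshold suits a tail harm better than changes and ANOVA, and it does not depend on who chose to report an event.

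**What to change.** 1. Keep the primary score, and state whether an in-range sample has a lower limit.
2. Add to the safety analysis, from scheduled laboratory values in both arms, the number and percentage of patients with any post-randomisation pre-dialysis potassium below 3.5 mEq/L. State the window: randomisation may precede the Week 0 HD3 session, while patiromer starts after it.
3. Add a second row for potassium below the protocol's own discontinuation level. Sections 6.7, 6.13 and 6.14 and schedule footnote 3 conflict on that level, and the study team must first reconcile them. No view is taken here on which is right; if the level proves to be 3.5, the two rows coincide.
4. Add the number and percentage with any on-treatment magnesium below the laboratory's lower limit. First confirm that the schedule's magnesium draws apply to both arms: section 6.8 sends usual care to sections 6.13 and 6.14, which do not mention magnesium.
5. Give n/N with exact 95% intervals, label the tables descriptive, and show the low-potassium table beside the primary result.

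The cost is a few lines of analysis text and one or two tables. No new samples are needed if the magnesium draws are confirmed for both arms. The drawback is wide intervals and possibly few or no cases.
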